This is a randomized, controlled crossover pilot study in 40 healthy men and women (50-75 y) to compare supplemental soluble fiber (35 g/d) + supplemental n-3 PUFA (6 g/d EPA+DHA), in quantities mirroring mean daily intakes associated with lower CRC risk, with a maltodextrin and corn oil control (placebo). Stool samples will be collected at the beginning, middle (day 15), and end of each of the two 30-day intervention periods. Using a novel, cost-effective, non-invasive approach, we will evaluate differences in global gene expression signatures in the stool exfoliome (i.e., sloughed colonic epithelial cells in stool) using RNA-Seq.³² We will focus on pathways related to colonic cell proliferation and apoptosis/ferroptosis, cell phenotype, and inflammatory response. Further, we will evaluate changes in gut microbial functional genes involved in butyrate production using droplet digital PCR (ddPCR). The collection of multiple samples over the intervention periods will provide a critical measure of longitudinal changes in response to the supplemental n-3 PUFA and fermentable fiber.

This pilot will be the first in humans to integrate and characterize the relationships between n-3 PUFA and fermentable fiber exposure that modulate programmed cell death and other CRC-related cell-signaling pathways through metabolic activities of the gut microbiome. Results of this controlled intervention will help to translate the current mechanistic knowledge from preclinical animal models to humans and to inform approaches for CRC prevention. Interrogating the stool exfoliome is a novel, cost-effective, non-invasive approach to studying effects of interventions on the human gut.

3. SPECIFIC AIMS, OBJECTIVES, ENDPOINTS:

Aim 1: To test in a pilot feasibility study, in humans, effects of supplemental dietary fiber (35 g) and EPA+DHA (6 g) vs placebo on mRNA expression in exfoliated colonic cells. We hypothesize that fiber and n-3 PUFA supplementation will uniquely influence colonocyte proliferation and programmed cell death-related gene expression and signaling pathways.

Aim 2: To test whether response to the intervention differs by gut microbial functional capacity related to fiber fermentation. We hypothesize that changes in colonocyte gene expression will be modified by the

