4. STUDY DESIGN

The study is designed as a randomized, cross-over, placebo-controlled dietary intervention of supplemental soluble fiber and supplemental n-3 PUFA compared to corn oil and maltodextrin control. We will randomize participants to one of the two treatment orders, either supplemental fiber and fat first followed by the placebo in the second period or the placebo first followed by supplemental fiber and fat. Each treatment will be 30 days in duration with at least a 60-day washout period between treatments. Stool samples will be collected at the beginning, middle (day 15) and end of each of the two 30-day intervention periods.

It will take participants at least 4 months to complete the trial. Details of the activities and timeline:

Activity	1-2 weeks before Day 0	DAYS in Period 1					at least 2 months (washout)	DAYS in Period 2				
		0	1 - 14	15	15 - 29	30		0	1 - 14	15	15 - 29	30
Info session and consent	1											
Fasting morning blood draw*	2							6				
Collect stool												
Deliver stool & get study supplements		3						6				
Take study supplements daily												
Collect stool												
Deliver stool & get study supplements				4						7		
Take study supplements daily												
Collect stool												
Fasting morning blood draw & deliver stool						5						8

*Visit 2: If results from liver/kidney functions test are abnormal, participant will not continue with study

Study Visit # = visits to Fred Hutch
= activities at home

4.a. Fiber and Fat Supplements The active treatment period will include supplemental soluble fiber (35 g/d) + supplemental n-3 PUFA (6 g/d EPA+DHA).

Supplemental Fiber: The soluble fiber with known fermentation profiles will be provided by Tate & Lyle, a well-established food and beverage ingredient company. For placebo, we will use maltodextrin provided in the same packaging and by the same company.

Supplemental n-3 PUFA: We will use a commercial fish oil supplement (Omega Cure, Omega3 Innovations), consumed as 2 vials daily. Each vial (11.75 g oil) delivers 3 g EPA +DHA in a 1:1 ratio. For placebo, we will use equivalent amounts of corn oil in visually identical packaging provided and by the same company.

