7. SPECIMEN AND DATA COLLECTION

7.a. Blood We will obtain 10-hour fasting blood samples at the beginning and at the end of each intervention period. The first sample will be sent to QUEST Diagnostics (a CLIA certified lab) for clinical chemistries (to confirm eligibility; see Section 6 for specifics). Participants will come to the Prevention Center at the Fred Hutch where certified personnel will collect four 10-ml vacutainers of blood; for plasma and serum. Specimens will be stored at -80°C.

7.b. Stool samples at three timepoints in each intervention arm, beginning, middle and end; for : a) exfoliated colonocyte transcriptome (mRNA) analysis, and b) fecal microbiome analyses. Participants

will collect small samples of stool into vials we provide that are pre-filled with RNAlater for microbial DNA,⁵⁹ RNAsheild for exfoliated colonocyte transcriptomics,⁶⁰ and in 95% ethanol for SCFA and future metabolomics measures.⁶¹ Human transcriptome profiles are stable for at least 60 h at 4°C prior to addition of RNAsheild solution and once RNAsheild solution is added, at -80°C for at least 2 yrs.^{48, 60}

7.c. Questionnaires: Dietary Assessment We will use an established, validated food frequency questionnaire (FFQ) to characterize food and nutrient intakes of the study participants over the 3 months prior to baseline to characterize habitual diets (typically low in n-3 PUFA and fiber and high in n-6 PUFA). **Health and Demographics** will also be collected. A **General Symptoms and Bowel Habits Questionnaire** will also be provided every time participants collect stool- this is a useful tool to determine intervention effects.

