9. DATA ANALYSIS

9.a. Data entry and quality assurance procedures. We will code and enter data from questionnaires, tracking forms, etc., and integrate with laboratory data, and monitor adherence to protocols for data entry, sample processing, storage, and analysis.

9.b. Aims testing, Overview: In **Aims 1 and 2** our analyses will investigate the response to the fiber and n-3 PUFA intervention at levels of **a) individual genes or variables** and **b) pathways and networks.** At the individual marker level (a) we will test genes and the butyrogenic potential (Aim 1 and 2) for differences due to intervention using univariate models, adjusting for appropriate covariates. At the pathway/network level (b), analysis will focus on hypothesized CRC pathways and employ gene-set ("global") enrichment analysis tests to evaluate changes in host gene pathways (Aim 1). When prior genetic/metabolic network structure is known within a pathway, the analysis will account for this.

Models: **a)** For single-gene/variable analyses (Aims 1 and 2), we use linear mixed models with a random effect for participant to account for the repeated measures of marker y during and at the end of each intervention. Fixed effects will include an indicator, *I*, for intervention as well as demographic covariates (e.g., age, sex, BMI) which will be tested by randomization and included where appropriate. Although randomization to intervention sequence should alleviate the potential for *differential* carryover effects between periods, models will include an indicator *S* of randomization sequence. Error terms ϵ_{ik} are assumed to be correlated within, and independent between, participants. In summary, models take the form $y_{ik} = \alpha_i + I_{ik} + S_i + \epsilon_{ik}$, where α_i is a random effect for subject. Robust standard errors will be used to test for differential effect of intervention, and all p values will be corrected for multiple testing by controlling the FDR using Benjamini-Hochberg⁷¹. **b)** For pathways, we will apply kernel association testing (KAT) procedures.^{72, 73} These multivariate methods allow for pathway-wide testing and modeling in a manner which extends gene-set style tests. They incorporate adjustment for covariates and generalize tools such as the globalTest,⁷⁴ used in genomics studies, and PERMANOVA,⁷⁵⁻⁷⁷ common to microbiome analyses. Network or structural relationships (e.g., metabolic) between genes in a pathway

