are easily incorporated into construction of a similarity/kernel matrix on which KATs are based^{72, 78}. These known (or estimated) interactions can enhance the KAT testing procedure to increase power.^{79, 80} Similar methods analyzing gene-gene networks have been successful in crossover dietary studies.⁸¹ We will account for the repeated-measures aspect of the crossover design in these models by applying a variant of family-based KAT.^{82, 83} Finally, longitudinal data collected on days 0, 15, and 30 of each period will be analyzed using a linear mixed model for each measure, as above. Terms for time and effect modification by intervention (time*intervention) will be added to this model if the data support autocorrelation within a measure across time. For longitudinal analyses of multivariate data (i.e., pathways/ gene-sets), we will test for longitudinal differences due to intervention by way of a repeated-measures KAT^{82, 83} and a variant of GSA.⁸⁴ We will consider effects of butyrogenic potential (defined as above and below the median; **Aim 2**) on host gene expression responses (**Aim 1**).

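### The single-measure longitudinal model includes time and time-by-intervention terms only if autocorrelation is found, a covariance criterion that cannot decide which mean terms are needed; without them the intervention coefficient mixes in the pre-supplement day-0 sample.

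*Combined protocol and SAP*

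**What the plan says.** Stool is sampled three times in each period (Section 7.b: "Stool samples at three timepoints in each intervention arm, beginning, middle and end"). Section 2 says the repeated sampling "will provide a critical measure of longitudinal changes in response to the supplemental n-3 PUFA and fermentable fiber".

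Section 9.b describes two uses of the single-measure mixed model:

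- **Base model.** It has a random participant effect, the intervention indicator I, the sequence indicator S and optional demographic covariates. It is used "to account for the repeated measures of marker y during and at the end of each intervention", which I read as days 15 and 30. Errors "are assumed to be correlated within, and independent between, participants", and robust standard errors are used.
- **Longitudinal model.** The "longitudinal data collected on days 0, 15, and 30 of each period will be analyzed using a linear mixed model" of the same form. Terms for time and its interaction with intervention are conditional: "time*intervention) will be added to this model if the data support autocorrelation within a measure across time".

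No test or threshold for autocorrelation is given, nor is the value of I on day 0. Nothing says how day 0 is treated when the time terms are left out. In the Section 4 activity table, the day-0 visit is where participants "Deliver stool & get study supplements".

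**The concern.** The rule uses a property of the errors to decide which terms belong in the mean. Correlated errors are already assumed, so finding autocorrelation adds nothing about whether expression changes over the period or changes differently on active supplement. For a single measure, that second question is the time-by-intervention term, which is the longitudinal response that Section 2 calls critical.

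The rule can remove this term measure by measure. What remains is an I coefficient that draws on a sample taken before any supplement of that period. I could then mean different things for different genes that share one multiplicity correction.

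**Working it through.** **Inputs from the plan.** Days 0, 15 and 30 in each of two periods; n=30, two-sided alpha 0.05 and a paired t-test (Section 9.c). The plan gives no figure for the longitudinal model. Its nearest figure is at least 80% power for effect sizes above 0.5. At exactly 0.5 the normal approximation gives 78.2% and the exact paired t-test 75.4%; the exact test reaches 80% at 0.53.

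**Assumptions of this check.** Complete, balanced data; residual SD 1; person-by-period SD τ of 0 or 0.5. Let d be the active-minus-placebo difference averaged over days 15 and 30, with no difference at day 0. Let t be a change from day 0 to days 15/30 common to both arms. The documents give no value for d in this model, or for t or τ.

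**Does autocorrelation track the mean effect?** In simulation with n=30, SD 1 per sample and no person effect:

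- AR(1) errors of 0.6 and no intervention effect gave a residual lag-1 correlation of about 0.58. The terms would be added with nothing to find.
- Independent errors and a true effect of 0.707 at days 15 and 30 gave about −0.03. The terms would be dropped although the interaction is real.

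**Time terms omitted, I=1 on all active-period days.** The coefficient is the mean of three active samples minus the mean of three placebo samples.

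- Expectation: (0 + d15 + d30)/3 = 2d/3. The change t cancels.
- Variance per person: 2τ² + 2/3. Using days 15 and 30 only, it is 2τ² + 1 with expectation d.
- At d=0.6, τ=0, the noncentralities are 0.4/√(0.667/30) = 2.68 and 0.6/√(1/30) = 3.29. On 29 df, power is 74% and 89%.
- At τ=0.5, they are 0.4/√(1.167/30) = 2.03 and 0.6/√(1.5/30) = 2.68, giving 50% and 74%.
- Null error stays at 5% (4.9–5.2% over 40,000 simulated trials per setting).

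**Time terms omitted, I=0 on day 0.** The coefficient is the mean of two active samples minus the mean of the other four.

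- Expectation: (d + t) − (0 + 0 + t + t)/4 = d + t/2.
- Variance per person: 1.125τ² + 0.75.
- With d=0, per-test error before Benjamini-Hochberg correction is:

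| t (residual SD) | 0 | 0.1 | 0.2 | 0.4 | 0.6 |
|---|---|---|---|---|---|
| τ=0 | 5% | 6% | 9% | 23% | 45% |
| τ=0.5 | 5% | 6% | 8% | 18% | 35% |

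**Time terms included, d=0.6, 28 df.**

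| Day-0 handling | Variance per person | Power, τ=0 | Power, τ=0.5 |
|---|---|---|---|
| Unconstrained: day 15/30 average minus day 0 | 3 | 45% | 45% |
| Unconstrained, linear time: day 30 minus day 0 | 4 | 35% | 35% |
| Day-0 difference constrained to zero | 2τ² + 1 − (2τ²)²/(2τ² + 2) | 89% | 76% |

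**Mixed-model check.** In 1,000 replicates with d=0.6, t=0.4, τ=0.5, the mean estimates were 0.405 (I=1), 0.801 (I=0), 0.597 (constrained) and 0.584 (unconstrained). The algebra gives 0.4, 0.8, 0.6 and 0.6.

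**How often would the terms be dropped?** This depends on a test the plan does not name. With no true AR(1), in 200 replicates per setting, a 5% likelihood-ratio test for AR(1) beyond a person effect (person SD 1) omitted them in 95% of measures at τ=0 and 70% at τ=0.5. A test for any within-person correlation omitted them in 0% at person SD 1 and 6–10% at person SD 0.5.

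**The case against.** - **Omission may be rare.** If autocorrelation simply means that a participant's repeated values are correlated, the terms would nearly always be added. This is a fair reading. The plan does not say, and the range from 0% to 95% is itself a reason to prespecify.
- **Dropping the terms costs no power against the plan's own alternative.** At τ=0 omission gives 74%, while the unconstrained interaction gives 45% or 35%. This stands: the 89% belongs to days 15/30 alone or to a constrained model that the plan does not contain. The omitted-term model, however, estimates a different quantity, and the point shows that the fix must handle day 0 properly.
- **The effect is tested elsewhere.** The base model uses days 15 and 30, and the pathway longitudinal tests carry no such condition. This is correct and limits the scope to the single-measure time course in a pilot.
- **The high error rates need I=0 on day 0 and a common shift.** Also correct: I=1 fits a time-by-intervention term better, t is assumed, and "all p values will be corrected for multiple testing by controlling the FDR using Benjamini-Hochberg", so per-test rates are not the plan's error measure. The effect on the FDR was not computed.
- **The factors 2/3 and t/2 need equal weighting.** With a fitted AR(1) of 0.3 or 0.6 they become 0.63 or 0.58, and 0.66t or 0.84t. With a fitted person-by-period effect (SD 0.5) the bias is 0.64t. But an AR(1) structure would not be fitted where autocorrelation is judged unsupported, and the plan has no person-by-period term. None of these changes reduces the distortion.
- **An omitted trend can leave a trace in residual correlation.** True in principle, but in the simulation the trace was near zero.

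**Conclusion.** The concern holds, with high confidence, and should be fixed. The inclusion criterion is the wrong kind for mean terms, and where it excludes them the day-0 sample distorts I under either coding: to two thirds of the day 15/30 effect, or by adding t/2. Those factors follow from algebra for balanced data under the plan's random-participant model. The powers and error rates rest on the assumed variances, effect size and t, and the frequency of omission is unknown. The finding is confined to the single-measure longitudinal analysis.

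**What to change.** In Section 9.b, for every measure:

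1. Always include categorical day and day-by-intervention, and state the value of I on day 0.
2. Treat day 0 as pre-treatment: constrain the intervention difference to zero there, or use the same period's day-0 value as a covariate. Either is acceptable; an unconstrained interaction is not a good substitute because of its low power.
3. Test the intervention contrast at days 15 and 30.
4. Use any autocorrelation check only to choose the covariance structure.

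The cost is SAP wording and a few degrees of freedom, with samples already scheduled. It stays this small only if the day-0 constraint or covariate is used.

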gut microbial capacity to ferment dietary fiber (i.e., SCFA-producing pathways), measured as butyrogenic potential. Σ (butyryl-CoA:acetate CoA-transferase (*but*) + butyrate kinase (*buk*) genes)/(total bacterial load 16S rRNA gene) assayed using digital drop PCR.

[figure not shown]
Objectives and Endpoints:

1. To determine whether the combination of supplemental dietary fiber and EPA+DHA vs placebo affects mRNA expression in exfoliated colonic cells. The endpoint is mRNA expression profiles in the exfoliome.
2. To determine whether gut microbial functional capacity related to fiber fermentation, as measured by presence of fiber-fermenting genes in stool bacteria, alters exfoliome mRNA expression response to the intervention on. The endpoint is mRNA expression profiles in the exfoliome.

Implications: This proposed pilot feasibility study will be the first controlled study in humans to integrate and characterize the relationships between n-3 PUFA and prebiotic fiber exposure that modulate programmed cell death/CRC-related cell-signaling pathways through changes in the gut microbiome. Results of this human mechanistic controlled intervention will help to translate the current mechanistic knowledge from preclinical animal models to humans and to inform approaches for CRC prevention. Also, importantly, we will further evaluate the utility of interrogating the exfoliome as a novel, non-invasive approach to studying effects of interventions on the human gut.

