incorporated into colonic cell membranes within 7 d.⁴⁷ 1-mo interventions with diet or aspirin result in measurable changes in colonocyte gene expression⁴⁸ and down-stream colon biomarkers.⁴⁹ Gut microbiome changes occur in 2-3 wks.^{3, 50, 51} Changes in gut mucosal cancer-risk biomarkers, the microbiome, and microbial metabolites were also seen in a short-term 2-wk intervention of fat and fiber.⁵² We hypothesize that changes in the gut microbiome influence colonic gene expression, thus conservatively we are using a 30-d period to allow sufficient time for both outcomes to change, while considering participant burden. Washout: The 60-d washout will ensure that residual intervention effects from the previous period are eliminated. As mentioned, the gut epithelium and microbiome change rapidly, but blood DHA+EPA clearance requires 45 d.⁵³

4.d. Monitoring and assessing adherence. Participants will meet with study staff routinely to assess any difficulties with study adherence. n-3 PUFA are rapidly incorporated into colonic tissue.^{54, 55} and there is high correlation between membrane PUFA and plasma phospholipid (PLFA) PUFA.^{56, 57} We will assess adherence to n-3 PUFA supplementation using plasma PLFA profiles (**Section C.4.a**) and by monitoring vial counts, calculating adherence % (vials supplied - vials returned/days elapsed).⁵⁸ Adherence to supplemental fiber will be monitored by study staff. Participants will be instructed to return unconsumed fiber packets for weighing and consideration in intake determination. During the intervention, participants will complete daily forms to monitor adherence to the supplements.³²

4.e. Summary of study activities and measures

Table 1. Study Activities and Measures

	Reason for Measures
Screening	
Screening questionnaire	Exclusion criteria
Information session	Informed consent
Baseline blood sample to Quest Diagnostics	Exclusion criteria (liver and kidney functions)
Health and Demographics questionnaire	Exclusion criteria
Anthropometrics	Exclusion criteria
Two Supplementation Periods	
Each 30 days each	
Cross-over (order randomly assigned) *	
Stool samples (6 total) Beginning, middle and end of each period	
For colonocytes	Global gene expression signatures in the exfoliome (using RNA-Seq)
For Microbial	Microbial DNA extraction, ddPCR and SCFA.
Bowel Habits & General Symptoms questionnaire	Intervention effects
Blood samples (4 total) Baseline & end of each period	Plasma phospholipid PUFA

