9.c. Power and sample size. This is a randomized, controlled crossover pilot feasibility study in 30 healthy men and women, designed to generate preliminary data to inform a larger human mechanistic study. Based on our previous experience, we are confident we will detect gene expression changes with the fiber + n-3 PUFA intervention. **Aim 1:** In our FlaxFx study³² with a similar crossover design, we detected differential expression of 32 genes between placebo and lignan extract (FDR<0.05) in exfoliated cells (n=42 participants). Given the impact of dietary fiber on multiple pathways in animal models,⁸⁵ we anticipate similar or better power in the current study. In addition, we also considered power for single-gene analysis in this crossover study (n=30). Using a 2-sided paired t-test at significance level alpha=0.05 and a range of effect sizes, conservative estimates are: power of at least 80% for effect sizes larger than 0.5. **Aim 2:** a power estimate for ddPCR data, based on differences in *but* gene abundance with low- ($4.96 \times 10^{11} \pm 3.22 \times 10^{10}$ copies/g feces) and high-fiber diets ($1.37 \times 10^{12} \pm 1.47 \times 10^{11}$) in healthy individuals (n=30),⁸⁶ at significance level alpha=0.05 and effect sizes larger than 0.8 , we estimate power at least 95 % to detect diet-related differences in this gene. We anticipate a similar distribution for *buk*.

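### Aim 2 asks whether a continuous ratio modifies the response, but 9.b cuts the ratio at the sample median, writes no modification term, and does not say which stool sample defines it

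*Combined protocol and SAP*

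**What the plan says.** Section 3 states Aim 2 as effect modification. The hypothesis opens "We hypothesize that changes in colonocyte gene expression will be modified by the", and the modifier that it goes on to name is "gut microbial capacity to ferment dietary fiber (i.e., SCFA-producing pathways), measured as butyrogenic potential". Sections 3 and 8.c define the ratio as the sum of the *but* and *buk* genes over total 16S load. Neither section names a threshold.

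The analysis of that hypothesis is the closing sentence of 9.b: "We will consider effects of butyrogenic potential (defined as above and below the median". The single-gene model in 9.b has a random subject effect, a sequence indicator, and an indicator "for intervention as well as demographic covariates (e.g., age, sex, BMI"). The only interaction named belongs to the longitudinal analysis: "Terms for time and effect modification by intervention (time*intervention) will be added to this model".

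Butyrogenic potential also appears in 9.b as an outcome: "we will test genes and the butyrogenic potential (Aim 1 and 2) for differences due to intervention". Table 1 in 4.e lists "Stool samples (6 total) Beginning, middle and end of each period", and nothing says which of these samples sets the median.

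In 9.c, the Aim 2 power of at least 95% is for the ability "to detect diet-related differences in this gene", meaning *but*.

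**The concern.** There are four linked gaps.

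- **Dichotomisation.** A continuous moderator is reduced to two groups with no stated reason. This discards information in a study whose sample size is limited by budget (section 11).
- **No test.** An analyst could fit an interaction, test each half separately, or compare the gene lists from the two halves. These answer different questions, and only the first tests modification.
- **No sample named.** The moderator is itself expected to respond to the intervention. A value taken after supplements have started would mix capacity with response.
- **No power for modification.** A reader may take the 95% in 9.c as covering Aim 2's hypothesis.

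The study is meant to inform a larger one. A null result from an undefined, inefficient comparison could wrongly steer that study away from fermentation capacity.

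**Working it through.** **1. The plan's own figure.** Inputs from 9.c are n = 30, alpha = 0.05 and effect size 0.8. As a two-sided paired t-test, the noncentrality is 0.8 × √30 = 4.38 on 29 df, and power is 98.8%. The stated figure of at least 95% reproduces. It is a within-person diet effect on *but*, not a test of modification.

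**2. What the test of modification is.** In a crossover, modification is an association between each person's active-minus-placebo response and that person's moderator B. It is a between-person comparison among 30 people, or 15 v 15 after a median split. At 80% power, 15 v 15 detects a difference of 1.06 SD of the within-person response.

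**3. Information kept by the split.** For a normal B, the correlation between B and its above-median indicator is √(2/π) = 0.798. The information kept is 0.798² = 0.637, as if 30 × 0.637 = 19.1 completers were used. Matching the continuous term at n = 30 takes about 30 / 0.637 = 47 completers by this formula, and simulation gives 48.

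**4. One worked value (Fisher z).** The continuous term has 80% power at r = 0.492: atanh(0.492) × √27 = 2.80, and 2.80 − 1.96 = 0.84. For the split, r falls to 0.492 × 0.798 = 0.393: atanh(0.393) × √27 = 2.16, and 2.16 − 1.96 = 0.20. Power is 57.8%.

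**5. Range.** The correlation r is an assumption, because the documents give none. The simulation used n = 30, normal B, linear modification, one response contrast per person, complete data, and a single unadjusted two-sided 0.05 test with ordinary standard errors. Losses are taken before rounding.

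| r | Continuous | Ranks | Median split | Loss, continuous to split |
|---|---|---|---|---|
| 0.3 | 37% | 35% | 25% | 13 points |
| 0.4 | 61% | 58% | 41% | 20 points |
| 0.49 | 80% | 77% | 58% | 22 points |
| 0.6 | 95% | 94% | 80% | 15 points |
| 0.7 | 99.5% | 99% | 94% | 6 points |

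**6. Other shapes** at r = 0.486, n = 30:

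| Shape of modification | Continuous | Ranks | Split |
|---|---|---|---|
| Saturating | 79% | 80% | 68% |
| Plateau above the median | 65% | 62% | 45% |
| Step at 25th or 75th percentile | 51–52% | 52% | 34–35% |
| Step at 67th percentile | 56% | 60% | 49% |
| Step at 60th percentile | 59% | 64% | 60% |
| Step at the median | 60% | 66% | 68% |

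**7. Robust standard errors.** Section 9.b plans them. With no modification and n = 30, a t-referenced HC1 test of a continuous term rejects 7.1% of the time, and HC3 rejects 5.1%. On ranks the figures are 6.1% and 4.7%. With HC3 at r = 0.486, ranks have 74% power and the split 55%. Ranks with HC3 reach 80% at r of about 0.52.

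**8. Multiplicity.** At a per-test level of 0.0005, standing in for FDR correction, the continuous term needs r = 0.68 for 80% power. The split then has 34%.

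**The case against.** The strongest reply is that this is a pilot feasibility study meant to produce preliminary data, and that 9.b promises only to consider these effects. A median split in that setting is inefficient but not invalid. That stands, and it limits the weight of any power shortfall. It does not excuse leaving the test undefined for one of two aims.

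Three stronger readings are tempting, and the documents do not support them.

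- **That the split takes the trial's best-case power from 80% to 58%.** The 80% is not a property of this trial. It comes from choosing r of about 0.49, close to where the loss is largest. At r = 0.6 the split itself has 80%. A saturating shape is also graded and loses only about 11 points.
- **That the 95% in 9.c is wrong.** It reproduces for what its sentence describes.
- **That the two halves would largely be active against placebo samples.** This would happen only if individual samples were pooled across treatments before the cut. Aim 2 treats capacity as a participant attribute, and in a crossover every completer supplies both kinds of sample, so a participant-level split cannot produce it. The low- and high-fiber *but* figures in 9.c come from an outside study in copies per gram and do not give the expected change in a ratio to 16S. What remains is that the defining sample is not named.

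Two practical objections to a continuous term also stand. It needs a small-sample correction under the planned robust errors. A replacement confined to single genes would drop modification at pathway level, which 9.b covers. Both are met in the change proposed.

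**Conclusion.** The concern holds and should be fixed. The firmest parts need no outside assumption: the moderator is continuous, 9.b cuts it at the median without a reason, no modification term is written, the defining sample is not named, and 9.c does not power modification.

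The size of the power loss is conditional. For linear modification and a roughly normal moderator the split keeps about 64% of the information. It costs 13 to 22 points for correlations of 0.3 to 0.6, and 6 points at 0.7. The cost is smaller for a saturating shape and turns into a gain of about 8 points (2 against ranks) for a step exactly at the median. Nothing in the documents gives a reason to expect a step there. The figures use one contrast per person in place of the full mixed model, ignore FDR correction except where stated, and do not cover the kernel tests.

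**What to change.** In 9.b, replace the median-split sentence with:

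> For Aim 2, butyrogenic potential B is one value per participant, from the day-0 stool of Period 1, before any supplement, entered on the rank scale. B and B × intervention are added to the single-gene model. The test of modification is the B × intervention term, using robust standard errors with a small-sample correction (HC3-type or CR2, with a t reference) and FDR control as planned. Pathway-level analyses (KAT and GSA) use the same continuous B as the modifier. Groups above and below the median are for display only.

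In 9.c, add:

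> The 95% does not cover effect modification. With 30 completers, a single unadjusted two-sided 0.05 test of B × intervention has about 80% power only if the correlation between B and within-person response is about 0.5, before FDR correction. A non-significant result is not evidence of no modification.

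The cost is one analysis definition and one added statement. The day-0 stool is already collected and ddPCR on stool is already planned, so no participants, samples or assays are added. The downside is up to about 8 points of power (2 on ranks) if the response truly steps at the median. The small-sample correction also costs a few points: at r = 0.486, ranks go from 77% to 74%.
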